6.2 FIDELITY

6.2.1 INTERVENTIONIST TRAINING AND TRACKING

Fidelity of the Intervention

We have structured the fidelity of the intervention using the NIH five category Treatment Fidelity Framework [38]. For category one, **treatment design**, both the intervention and control condition will receive different content but will be the same length, number, and duration of contact over time. The bilingual interventionists will have experience teaching health interventions, and the theoretical model is clearly articulated. For category two, **training**, the bilingual interventionists will be trained by the PI and teach back the intervention to the PI. For category three, **delivery of the intervention**, integrity will be assessed by observation of two randomly selected classes per month by the project manager who will use a checklist to score classes based on pre-identified content, and drift will be defined as teaching less than 80% of protocol content. If drift occurs, the bilingual interventionists will be retrained until the protocol is followed consistently. We will also use a list of behavioral indicators to assess the interventionists' skills in facilitating classes, engaging mother-child dyads, role playing, problem solving, providing positive feedback, and goal setting. Retraining will be provided if problems are found. In our pilot study [23], we had little difficulty in maintaining consistency of the intervention. The bilingual interventionists will collect data on attendance at each class, reasons for non-attendance, and make-up classes provided. Category four, **receipt of treatment**, will be evaluated during the class by the bilingual interventionist who will assess understanding and answer all questions. Category five, **enactment of intervention skills**, will be evaluated during the six monthly continued support classes by the bilingual interventionist.

6.3 MEASURES TO MINIMIZE BIAS: RANDOMIZATION AND BLINDING

After enrollment and baseline assessment, dyads will be randomized to either the intervention or control group using a computer-generated randomization table, stratifying by BMI group, overweight ($25 - 29.9 \text{ kg/m}^2$) and obese ($\geq 30 \text{ kg/m}^2$), and utilizing blocking to help ensure balance between the groups. Mothers will be informed of their group assignment by telephone. We have not included fathers, as in previous studies in this population, because the majority of fathers work 6 days a week and cannot attend class [7, 23]. Data collection research assistants will be blinded to group status.

6.4 STUDY INTERVENTION/EXPERIMENTAL MANIPULATION ADHERENCE

See 6.2.1 for details

6.5 CONCOMITANT THERAPY

N/A

6.5.1 RESCUE THERAPY

N/A

7 STUDY INTERVENTION/EXPERIMENTAL MANIPULATION DISCONTINUATION AND PARTICIPANT DISCONTINUATION/WITHDRAWAL

7.1 DISCONTINUATION OF STUDY INTERVENTION/EXPERIMENTAL MANIPULATION

The intervention will only be discontinued after consultation with the study team and the program officer.

7.2 PARTICIPANT DISCONTINUATION/WITHDRAWAL FROM THE STUDY

Participants are free to withdraw from participation in the study at any time upon request.

An investigator may discontinue a participant from the study for lost-to-follow up and unable to contact subject.

The reason for participant discontinuation or withdrawal from the study will be recorded. Subjects who sign the informed consent form and are randomized but do not receive the study intervention may be replaced. Subjects who sign the informed consent form, and are randomized and receive the study intervention, and subsequently withdraw, or are discontinued from the study will not be replaced.

7.3 LOST TO FOLLOW-UP

A participant will be considered lost to follow-up if she fails to return for scheduled visits and study staff are unable to contact the participant after at least 3 attempts.

The following actions must be taken if a participant fails to return for a required study visit:

The site will attempt to contact the participant, reschedule the missed visit, counsel the participant on the importance of maintaining the assigned visit schedule and ascertain if the participant wishes to and/or should continue in the study.

Before a participant is deemed lost to follow-up, the investigator or designee will make every effort to regain contact with the participant (where possible, 3 telephone calls. These contact attempts will be documented in the participant's medical record or study file.

Should the participant continue to be unreachable, he or she will be considered to have withdrawn from the study with a primary reason of lost to follow-up.

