Weight management studies typically have attrition rates ranging from 10%-30% [19]. To strengthen retention, our classes will be interactive, with culturally and linguistically tailored content developed to engage and sustain the interest of the mother-child dyads. Mothers who miss class will be offered a make-up class over the phone, and reminded when the next class will be held. Additional incentives will include childcare for other children who accompany mothers and their 3-5-year-olds to class and recipes and handouts in Spanish on how to improve their children's nutrition and physical activity behaviors. Mothers will be asked for telephone numbers of several family members and permission to call them if we cannot reach them. We will be as flexible as possible in scheduling enrollment and data collection appointments and provide tokens of appreciation such as birthday cards and a quarterly newsletter with updates on the study. Mothers in both groups will receive \$25 after each data collection. These approaches proved successful in our pilot study with Hispanic mothers with limited English proficiency, where attrition was only 9%-15% [23] and those mothers who stopped coming had moved out of the state. We will make every effort to keep our attrition rate lower than the projected 15%. If retention rates drop below 85%, we will contact the mothers to ask why they stopped coming and develop strategies to meet the needs of each mother to assist them to continue in the study if possible.

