mediator (M), which in turn influences the outcome (Y). Models will be conceptualized for each measure of weight and adiposity for mothers identified in Aim 1 (Y) and for each proposed mediator (M), relative to the randomized intervention group (X). For each model, an effect ratio (defined as the ratio of the indirect effect to the total effect, yielding the proportion of the effect that is mediated) and its bootstrapped distribution will be computed to assess the strength of mediation. Mediators (M) to be tested are improvements in health behaviors and self-efficacy. For example, we will analyze the effect of the intervention on change in maternal self-efficacy from baseline to Time 2, and, in turn the effects of this change in maternal self-efficacy at Time 2 on change in maternal BMI at Time 3.

Sensitivity analyses for Aims 1-3. Site will be included in all the models, and we will look for evidence of differential effects across cohort or site. The primary analyses use all available data, but if there is evidence of differential missingness by treatment group, we will use imputation methods as a sensitivity analysis.

Aim 4: We will calculate the incremental cost-effectiveness of the intervention, carried out from society's perspective as:

$$CE_{ij} = \frac{C_i - C_j}{E_i - E_j}$$

Where C is cost over the time period of the study; E is effectiveness measured by the outcomes; *i* refers to the intervention and *j* refers to the control group. We will calculate cost-effectiveness for the principal outcomes of the study; including cost per unit of BMI reduction, and cost per unit of improvement on the nutrition and physical activity self-efficacy scales. We will carefully track and calculate the costs of the program intervention activities and the control group activities, in order to measure the differences between the costs in the two groups. These costs will include hiring interventionists for all aspects of the Healthy Mothers-Healthy Children intervention. We will track the time invested in the program by participants in both the intervention and control group and calculate the value of time (opportunity cost) relative to the mothers' average income.

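### Section 7.3 treats a participant who stays unreachable after a missed visit as withdrawn from the whole study and does not say that Time 3 is still attempted

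*Combined protocol and SAP*

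**What the plan says.** Section 7.3 has three parts.

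- **Definition:** "A participant will be considered lost to follow-up if she fails to return for scheduled visits and study staff are unable to contact the participant", with a minimum of three attempts. Visits are plural here.
- **Procedure:** "The following actions must be taken if a participant fails to return for a required study visit". One visit is enough to start it. The site tries to make contact, reschedule and counsel.
- **Consequence:** "Should the participant continue to be unreachable, he or she will be considered to have withdrawn from the study", with lost to follow-up as the primary reason.

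Section 7.2 covers the same situation permissively: "An investigator may discontinue a participant from the study for lost-to-follow up and unable to contact subject". Neither section mentions Time 3 for a dyad lost at Time 2, or separates loss of contact from withdrawal of consent.

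The schedule (1.3 and 8.1) has two follow-up assessments: Time 2 at 9 months, and Time 3 at 15 months after six months without staff contact. On the analysis side, 9.3 specifies intent-to-treat with all subjects. Section 9.4.10 models the outcome at each of three time points with time as categorical, and states: "The primary analyses use all available data".

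**The concern.** With only two follow-up assessments, being coded as withdrawn at Time 2 puts half of a dyad's follow-up at risk. The label comes from the mother's non-contact, but the child's primary outcomes go with hers. The six months of planned silence before Time 3 offer no routine occasion on which such a dyad would come back into view.

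The analysis has no need of this closure. A dyad with Times 1 and 3 informs the Time 3 versus Time 1 comparison even when Time 2 is absent. If the dyads that cannot be reached at Time 2 differ in outcome from those that can, a Time 3 value that was never sought cannot be restored later. The imputation sensitivity analysis in 9.4.10 is conditional on evidence that missingness differs by treatment group, so outcome-related loss at equal rates would not trigger it.

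**Working it through.** **1. What happens to a dyad that misses Time 2.**

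- Mother is reached: 7.3 reschedules the visit, and 5.5 leaves time for make-up data collection. Nothing is lost.
- Mother is not reached: 7.3 counts her as withdrawn from the study. Whether Time 3 is attempted is not stated either way.
- A Time 3 value is obtained anyway: the 9.4.10 model uses it.

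The gap is in the second case only.

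**2. The plan's own figures (9.2).** Enrolment: 250/(1 − 0.15) = 294.1, against the stated 294; conversely 294 × 0.85 = 249.9. So 294 − 250 = 44 dyads are already budgeted as lost.

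Power: 2-df group-by-time test at two-sided 0.05, three time points, compound symmetry, SD 1. The pattern of means is not given, so I assume no baseline difference and the same standardised difference δ at Times 2 and 3. The noncentrality is then nδ²/[3(1 − ρ)], with n = 125 per group and 2 and 247 df.

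- Mothers' BMI (δ 0.53, ρ 0.25): 125 × 0.2809/2.25 = 15.6, power 95.0%
- Children's BMI percentile (0.59, 0.30): 125 × 0.3481/2.1 = 20.7, power 98.7%
- Conservative case (0.45, 0.20): 125 × 0.2025/2.4 = 10.5, power 83.2%

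These agree with the stated 95% and 80% levels, the first of them only just.

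**3. Simple precision estimate.** The documents do not say how many dyads would be closed at Time 2 or how many could be found later. Assume 30 of the 44 are closed by Time 2 and a third to a half of these are reachable at Time 3: 30 × 1/3 = 10 and 30 × 1/2 = 15. Dyads assessed at Time 3 rise from 250 to 260-265. The standard error ratios are √(250/260) = 0.981 and √(250/265) = 0.971, a reduction of about 2-3%.

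**4. Mixed-model version, conservative case.** Assume 147 per group at baseline, the full 15% missing Time 2 (22 per group), no other losses, and a share q of those 22 seen at Time 3. Contrast power, before the Hochberg correction, is Φ(0.45/SE − 1.96).

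| q | Time 3 n per group | SE, Time 3 vs Time 1 | Power, contrast | Power, interaction |
|---|---|---|---|---|
| 0 | 125 | 0.1552 | 82.6% | 86.7% |
| 25% | 130.5 | 0.1531 | 83.7% | 87.2% |
| 50% | 136 | 0.1511 | 84.6% | 87.6% |
| 100% | 147 | 0.1475 | 86.2% | 88.4% |

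The largest possible gain on the contrast is 86.2 − 82.6 = 3.6 points. If only 5% miss Time 2, the range is 85.2% to 86.2%. At q = 25% (5.5 per group, 11 dyads) the contrast's standard error falls by 1 − 0.1531/0.1552 = 1.4%. That is a little less than step 3 suggests, because the contrast also carries baseline variance that recovery does not change. The interaction power at q = 0 exceeds the 83.2% of step 2 because every dyad's baseline enters the model and a large-sample reference distribution is used.

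**5. Bias.** For a fraction f unseen at Time 3 in each group, the group difference among those seen is shifted by f × (gap in intervention − gap in control). The gap is the mean of seen minus unseen dyads, given baseline. At f = 0.15 this is 0.15 SD for each SD by which the two gaps differ. It is zero if the gaps are equal. The documents give no figure for either gap.

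**The case against.** The strongest reply is that the text is silent on Time 3 rather than wrong, and that a reader may infer more than it says. Five stronger readings are tempting.

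- *Missing Time 2 removes Time 3.* Not supported. A mother who is reached is rescheduled, 7.2 is permissive, and loss of Time 3 is an inference from the withdrawal label.
- *One missed visit and three unanswered calls suffice.* This is one reading. The definition uses the plural and requires that "study staff are unable to contact the participant after at least 3 attempts", and the procedure adds that "the investigator or designee will make every effort to regain contact with the participant (where possible, 3 telephone calls". Three calls is therefore not a ceiling. Family contacts are also collected for this situation: "Mothers will be asked for telephone numbers of several family members and permission to call them if we cannot reach them". Their absence from 7.3 is a missing cross-reference.
- *Dropping out of classes leads to withdrawal.* Not supported. Missed classes have their own handling in 5.5, 6.1.1 and the monitoring plan (make-up by telephone, reminders, calls to ask why), and none of it ends in withdrawal.
- *Lost dyads are mainly the disengaged.* No source says so. Section 5.5 reports that pilot mothers who stopped coming had moved out of state, and 6.1.1 reports equal attrition between groups in previous studies. Recovery could therefore be lower than assumed.
- *Section 7.3 contradicts intent-to-treat.* It does not. Sections 9.3 and 9.4.10 govern data that have been collected, and 7.3 excludes none of those.

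All five limits stand. What remains is that the consequence in 7.3 is mandatory, covers the whole study, and is not reopened at Time 3 anywhere.

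**Conclusion.** The concern holds as a gap in the follow-up rule. Section 7.3, applied literally to a dyad not reached at Time 2, permits Time 3 to be forgone although the planned model would use it. The plural and singular triggers in the same section also disagree.

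The size is modest. The precision gain is about 2-3% of the Time 3 standard error if 10 to 15 dyads are recovered. The upper limit of 3.6 power points in the conservative case needs all 15% attrition to fall at Time 2 and every such dyad to be found. Recovery rates are assumed throughout. The stated sample size and power do not change.

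The better reason to act is to limit avoidable missing data, and with it potential attrition bias at Time 3. The direction and size of that bias cannot be derived from the documents.

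**What to change.** Amend 7.3 as follows, and align 7.2:

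1. Reconcile the definition with the procedure, so that it is clear which visits count and whether one is enough.
2. Record a missed Time 2 without contact as a missed visit, not as withdrawal.
3. Contact every randomised dyad again for Time 3, in both arms and by the same procedure, including through the family contacts in 5.5. The exceptions are dyads that have withdrawn consent or been withdrawn under another protocol rule, such as the pregnancy rule in 8.3.9 or the underweight-child example in Section C of the monitoring plan. Those rules are left as they are.
4. Assign lost to follow-up only after the Time 3 attempts fail, and limit discontinuation for loss of contact under 7.2 to that point.

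Make these attempts when Time 3 is being scheduled, so that the six months without staff contact are kept. In reports, call the recovered dyads assessed at Time 3 rather than completers, because 4.4 requires all three assessments for completion.

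The cost is amendment wording, a few more calls per missed dyad by existing staff, and final disposition known up to six months later for some dyads.

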8 STUDY ASSESSMENTS AND PROCEDURES

8.1 ENDPOINT AND OTHER NON-SAFETY ASSESSMENTS

Variables and Their Measurement	Respondent	Time 1	Time 2	Time 3
Short Acculturation Questionnaire for Hispanics	Mother	X		
Health History Questionnaire	Mother	X		
Sports Physical	Mother	X		
Adiposity (Primary Outcomes)				
Waist Circumference	Mother/Child	X	X	X
Triceps and Subscapular Skinfolds	Mother/Child	X	X	X
Weight Status (Primary Outcomes)				
Height/Weight	Mother/Child	X	X	X
BMI/BMI Percentile	Mother/Child	X	X	X
Health Behavior				
Adult Health Behavior Survey	Mother	X	X	X
Health Promoting Lifestyle Profile II	Mother	X	X	X
24-hour Food Recall for 3 days	Mother for Self/Child	X	X	X
Accelerometer for 7 days	Mother for Self/Child	X	X	X
Self-Efficacy				
Eating Self-Efficacy Scale	Mother	X	X	X
Exercise Self-Efficacy Scale	Mother	X	X	X
Demographic Data	Mother for Self/Child	X		
Health History Update Questionnaire	Mother for Self/ Child		X	X
Process Evaluation Bi-Monthly	Project Manager			
Exit Interviews	Mother			X

Time 1 (0 months [baseline]); Time 2 (9 months [completion of the intervention]); Time 3 (15 months [after 6 months with no contact from the study staff]).

8.2 SAFETY ASSESSMENTS

N/A

8.3 ADVERSE EVENTS AND SERIOUS ADVERSE EVENTS

8.3.1 DEFINITION OF ADVERSE EVENTS

See Data Safety Monitoring (DSMP) Below

8.3.2 DEFINITION OF SERIOUS ADVERSE EVENTS

See DSMP Below

8.3.3 CLASSIFICATION OF AN ADVERSE EVENT

See DSMP Below

8.3.3.1 SEVERITY OF EVENT

See DSMP Below

8.3.3.2 RELATIONSHIP TO STUDY INTERVENTION/EXPERIMENTAL MANIPULATION

Data and Safety Monitoring Plan (DSMP)

Study Identification

NIH Study Number – 1R01NR017199-01

Study Title – Healthy Mothers: Healthy Children: An Intervention with Hispanic Mothers and their Young Children

Principal Investigator – [name], RN

Study Overview

The overall goal of this project is to determine whether a nutrition and physical activity education, coping skills training, exercise program, and a home-based exercise program will decrease adiposity and weight, and improve health behaviors and self-efficacy in mothers of Hispanic heritage and slow excessive adiposity and weight gain in their 4-year old children. The DSMP outlined below for the proposed study will adhere to the protocol approved by The University of North Carolina at Chapel Hill (UNC-CH) Institutional Review Board (IRB) and the National Institutes of Health (NIH) and the National Institute of Nursing Research (NINR).

SECTION A. Monitoring Entity

Considering the study rationale, population, procedures, and the risk: benefit profile as outlined, the overall risk level for participation in this study is classified as no more than minimum risk.

1) Individual Roles and Responsibilities

An Executive Committee will be formed to oversee the conduct of the study. The committee will be comprised of nine members: [name] (Principal Investigator [PI]) and the Study Investigators, Drs. [name], [name], [name], [name], [name], [name], [name], and [name]. The PI will Chair the Committee, which will meet monthly to review the activities of the study including management, personnel, recruitment, performance, and any emerging problems.

The Independent Monitor (ISM) for this study will be [name]. [name] has been the Inaugural Assistant Director for Operations of the Office of Human Research Ethics at UNC-CH, which was preceded by six years as the IRB Chair and Chair of the School of Nursing (SON) IRB. [name] is not associated with this research project and thus works independently of the PI. [name] is not one of the key personnel involved in this grant. She is qualified to review the participant safety data generated by this study because of her unique expertise in human research ethics and serving as the ISM on multiple previous studies.

B. Procedures for Safety, Risk, and Confidentiality

1) Monitoring Study Safety

From the initial screening of participants by inclusion and exclusion criteria to the informed consent process to the provision of participant study instruction to staff training in Good Clinical Practices (GCP) and regulations pertaining to the Conduct of Human Participant Research to weekly contact with participants to internal monthly quality control audits and protocol fidelity monitoring to the real-time review of adverse events (AE) and serious adverse events (SAEs) by the PI, Study Investigators and the ISM, the study will be carefully overseen.

Drs. [name], [name], [name] (Study Statistician), [name], [name], [name] (ISM) [name], [name], [name], and [name] will review the data for this study quarterly. We will examine participant accrual and adherence to the protocol regarding demographics and inclusion and exclusion criteria, and compliance of treatment, AE and SAE rates quarterly, and report regarding statistical power implications of dropouts and missing data annually.

Data on compliance to the intervention will be collected weekly by the Project Manager (PM) and reviewed quarterly by the Study Investigators, Study Statistician, and the ISM. Compliance on the part of participants will be evaluated by attendance and process evaluation as outlined in the study. If intervention attendance drops below 85%, the mothers who have stopped coming will be called to ask for feedback. Using information gained from these phone interviews, the PI will schedule a meeting with the Study Investigators and the ISM to discuss methods for improving compliance.

As in previous studies, the PI and the Study Statistician will oversight and train the PM to establish a system to ensure the verification of source data compliance. The source data will include original records necessary for the reconstruction and evaluation of the clinical trial. It will be clear who documented the data, documentation will be readable, signatures identifiable, contemporaneous, original copy, accurate and consistent, long-lasting and durable, available and accessible, complete, consistent, credible, and corroborated. All data will be first checked by two separate Research Assistants (RAs) at different times. REDCap will be used as our Research Electronic Data Capture System. The PI has been trained in REDCap and has used it in previous studies and REDCap is supported by UNC-CH. The REDCap database creation will be overseen by [name] (Study Statistician). [name] will run comparisons and trained RAs will compare against source data and make corrections as needed. A data log book will be created to establish an audit trail for compliance as the PI has done in previous studies.

Drs. [name], [name], [name], [name], [name], [name], [name] [name], and [name] will personally conduct and supervise the study. We will register the study in ClinicalTrials.gov. We will follow the protocol and ensure all study staff follow the protocol. All staff assisting with the study will be informed of their obligations. We will ensure informed consent, approval and reporting. We will report to the NIH/NINR Program Officer, [name], any AEs or SAEs. We will maintain adequate records and make them available for inspection. We will ensure initial and continuing review by UNC-CH IRB and will report all changes to research and involving risks to subjects, and not make any changes without IRB approval except where necessary to eliminate immediate hazards. All of the study team are CITI trained and follow the Good Clinical Practice (GCP) Guidelines.

2) Minimizing Research-Associated Risk

Diligent study safety monitoring will be conducted by the PI as follows. The PI will work with the IRB to set up a schedule of selected cases to ensure compliance with IRB requirements. The PI and Study Investigators have worked closely with the IRB in previous studies providing the data requested for audits as required. Risks to human subjects will be minimized through the utilization of established protocols that have worked well in previous studies. We are aware that AEs and SAEs may occur and an Adverse Event Monitoring Committee will monitor their occurrence and the overall risk of the study to both mothers and their children.

Mothers who express fatigue during sessions will be excused from the session and another time convenient for them will be scheduled to make up the content. If a mother expresses fatigue during data collection, the data collection session will be terminated immediately, and a follow-up appointment scheduled. No mothers expressed fatigue in the PI's previous studies. It is not anticipated that the classes or data collection will cause any adverse effects, but participants will be encouraged to identify any concerns to the study staff. All mothers and their children will continue to receive routine medical care from their health care providers throughout the study. Referral to their health care provider will be made if any adverse effects are self-identified. There are no

known social or legal risks for the mothers who consent to participate for themselves and consent for their children in this study. There will be adequate time for mothers to ask questions, and they will be given phone numbers to reach the PI and PM if they have any further questions or concerns.

Institution-Wide Assurances will be assured by the use of the protocol, which will be conducted fully in keeping with the signed PI in accordance with UNC-CH IRB, NIH, and NINR.

3) Protecting Confidentiality of Participant data Participant Screening and Enrollment

All data from participants screened for the study will be entered into the REDCap electronic study database. Designated research staff will collect, gather, and enter required data (written informed consent, Health Insurance Portability and Accountability Act (HIPAA) authorization, medical history and demographics) onto study data forms. Screened patients who do not meet study eligibility will have specific screening data entered into the study database. The collected data will be helpful in examining the patient population and feasibility of enrollment criteria and will include gender, age, race and reason for exclusion. All dates will be shifted and other Personal Health Information (PHI) will be removed from the study database upon study completion. All data obtained from this study will be used for research purposes only and will comply with Federal HIPAA regulations.

Written informed consent will be obtained from each participant at entry into the study. Informed consent is obtained by the following process. The participant will be read the study consent form in Spanish. The bilingual PM or trained bilingual RA will meet with the participant to review the form, to confirm the participant's understanding of the study, and to answer any questions that the participant might have. Once the participant demonstrates understanding of the study and agrees to participate in the study, the consent will be signed in the presence of the bilingual PM or bilingual RA. The IRB will oversight yearly renewal of consent forms and the PI and the research team will provide data as requested for the renewal.

Confidentiality will be protected through coding mechanisms. The names of all participants will be removed from the data and a code number assigned. Each participant's identifying data will be separated from the study data, and the key identifying code numbers and the participant's identification will be kept by the PI in a password protected computer in a locked office that only the PI and the PM will have access to. Data will be reported in aggregate form without identifying information by site or individual. All research study personnel will be trained in IRB and HIPAA guidelines to maintain the security and confidentiality of the data. Mothers will be made aware of the precautions that the research team will take in keeping their data confidential. All identifying information will be destroyed at the earliest possible time following completion of the study. Publications arising from the study will not contain personal information. All data will be analyzed by groups, with no potential for individual participants to be identified.

Case Report Forms. All proposed study specific case report forms (source documents) for data collection will be designed by the PI and PM in concert with the Study Statistician and transferred by the PM into electronic Case Report Forms (eCRFs) for use in the study's REDCap database. These study specific eCRFs source documents (study logs for correspondence, contacts, compensation and other forms such as pre-eligibility screens) will be coded by the participant's unique study identification number for all data collected including study instruments will be maintained in the participant research record that will be made accessible to study monitors. Completed instruments that require a signature on a paper CRF will be scanned and uploaded into the study database as well as maintained on file in accordance with UNC-CH policies and applicable Federal Regulations for the Conduct of Human Participant Research.

Binders. The PM will prepare and maintain a participant-specific binder for each participant containing all non-eCRFs records. A regulatory file will also be maintained to include the IRB approved Protocol, original

Informed Consent documents, HIPAA forms and other study-related regulatory documents. All paper research records and CRFs will be maintained in a locked file cabinet in a secure facility within the SON. Access to the research records, study database and PHI will be restricted to study personnel as approved by the PI and IRB. As with all studies conducted at the UNC-CH, this study is also eligible for a random audit by Office of Compliance.

Data Processing. This study will use Research Electronic Data Capture (REDCap) for data capture and management.

Data Security. Ensuring data security, compliance with 21 CFR 11 and maintaining the integrity of PHI is a top priority.

Data Entry. Each participant will be assigned a unique study identifier, all PHIs will be masked, and data exports will be limited to the PI, the PM, and Study Statistician for generating reports and the conduct of statistical data analysis.

Data Monitoring. Ongoing quality control procedures will be implemented for data collection, storage and processing. The PM will conduct monthly monitoring of the study database and generate a report for the PI to review at team meetings. Standing agenda items for these meetings will include participant recruitment and retention, AEs, SAEs, protocol deviations, data integrity and overall study conduct.

Database Protection. The REDCap database will be secured with password protection. The informatics manager receives only coded information, which is entered into the database under those identification numbers. Electronic communication with outside collaborators involves only unidentifiable information.

SECTION C. Procedures for Identifying, Reviewing and Reporting Adverse Events

1) Identifying. Potential risks identified for participants are outlined in the Protection of Human Participants and will also be outlined in the IRB approved informed consent document.

[name] (Chairperson of UNC-CH School of Nursing Human Participant Research Review Committee and ISM) will chair the Adverse Event Monitoring Committee, which will include Drs. [name] (PI), [name], [name] (Study Statistician), [name], [name], [name], [name], [name], and [name] and the PM. The committee will meet every 3 months or more often as warranted, to review data related to AEs and SAEs and assure that safety standards are maintained. Despite usual precautions, we are aware that AEs and SAEs may occur, and this committee will monitor their occurrence and the overall risk of the study to both mothers and their children. We will develop a system to test whether abnormalities are equally distributed between the intervention and equal attention control groups. Data will be presented to the committee if a significant increase in abnormalities is noted. The committee will be asked to establish measurable standards that must be met before they recommend modification of the study on the basis of safety. These standards will be clearly delineated in the meeting minutes and approved by the committee. The committee will provide the PI with recommendations regarding problems that would require modification for safety reasons. Minutes of each meeting will be kept, and all actions and decisions documented to establish an audit trail. [name], the Study Statistician, will be instructed by the PI to prepare the randomization plan for the study and prepare reports for the committee under the direction of [name] (Chair and ISM).

2) Reviewing. Adverse events will be assessed and graded as follows.

Expected/Anticipated—Identified in nature, severity, or frequency in the current protocol, informed consent, investigator brochure, or with other current risk information.

Unexpected/Unanticipated—Not identified in nature, severity, or frequency in the current protocol, informed consent, investigator brochure, or with other current risk information.

More Prevalent—Occurs more frequently than anticipated or at a higher prevalence than expected.

Serious—Results in death, is life threatening, requires inpatient hospitalization or prolongs existing hospitalization, results in persistent or significant disability/incapacity, cancer, overdose, or causes a congenital anomaly/birth defect.

The relationship of AE to study participation will be determined by the Adverse Monitoring Committee as follows.

Unrelated—There is not a reasonable possibility that the adverse event may have been caused by the drug, device or intervention.

Possibly Related—The adverse event may have been caused by the drug, device, or intervention, however there is insufficient information to determine the likelihood of this possibility.

Related—There is a reasonable possibility that the adverse event may have been caused by the drug, device or intervention.

3) Reporting. The PI will responsible for ensuring that all AE and SAEs are reported to the NIH/NINR ([name]) and UNC-CH's IRB in compliance with their requirements.

Any AE will be reported by the PI to the Adverse Event Monitoring Committee within one week. An incident report will be created and sent by electronic email by the PI to Drs. [name], [name] (Study Staistician), [name], [name], [name] (ISM) [name], [name], [name], and the PM. The PI will follow-up with the mother and child and will prepare a report. The AEs will be reviewed every three months and a report prepared for the Human Participants Committee and [name] at NIH/NINR. Process notes will be kept concerning any decisions.

Any SAE or deaths that occur during the study will be reported by telephone immediately to the Human Participants Research Review Committee Chairperson and [name] (ISM) and to NIH/NINR ([name]). An incident report will be sent by electronic mail by the PI to Drs. [name], [name], [name], [name], [name], [name], [name], and the PM. The PI will follow-up immediately with the mother and child to investigate and prepare a report for all members of the Human Participants Committee and comply with all regulations regarding the reporting of SAEs. If the PI is unavailable, [name] will be on-call in the PI's absence. The PI or [name] in the PI's absence will be responsible for complying with all regulations concerning the reporting of a SAE and will prepare a full report for NIH/NINR. It is not expected that the committee will be involved in the decision to terminate the intervention for a study participant related to any adverse event. The PI will meet with the Study Investigators and the PM and seek input from the Program Officer ([name]) and [name] (ISM). Process notes will be kept concerning any decisions.

4) Examples of Potential Reportable Adverse Events. An AE is reportable if it meets all of the following criteria: 1) is unexpected 2) is related and/or possibly related, and 3) is serious and/or suggests that the research places subjects or others at a greater risk of physical or psychological harm than was previously known or recognized. Additionally, per UNC-CH's policy all participant deaths, protocol deviations, complaints about the research, and breaches of confidentiality are reportable events.

An example of an AE would be that a 3-5-year old child decreases from the 25th percentile (normal or healthy weight) to below the 5th percentile (underweight) at the next data collection. The steps to be taken include withdrawing the child and their mother from the study. The PI will immediately contact [name] (Pediatrician), [name] (ISM), the IRB Contact person, and Program Officer [name] at NIH/NINR. The PI will assist the mother to call her Pediatrician and set up an immediate appointment to have her 4-year old child evaluated and ensure that follow-up was received.

An example of an SAE would be the death of a participant from acute renal failure, which although would be viewed as unexpected and unrelated to the intervention is nonetheless a reportable serious event. No further steps would be taken except to review, grade and report the event.

5) Safety Review Plan. Study progress and safety will be reviewed monthly (and more frequently if needed). Progress reports, including participant recruitment, retention/attrition, and AEs will be provided to [name] (ISM) following each of the monthly reviews. An annual report will be compiled and will include a list and summary of AEs and SAEs. In addition, the annual report will address (1) whether adverse event rates are consistent with pre-study assumptions; (2) reason for dropouts from the study; (3) whether all participants met entry criteria; (4) whether continuation of the study is justified on the basis that additional data are needed to accomplish the stated aims of the study; and (5) conditions whereby the study might be terminated prematurely. The annual report will be signed by [name] (ISM) and will be forwarded to the IRB and NIH/NINR. The IRB will review progress of this study on an annual basis.

SECTION D. Multi-Site Monitoring and Compliance

This is not a multi-site study.

SECTION E. Assessment of External Factors

